## ii) Secondary

Analysis of recall rate and rate of disagreements between intervention and control group will use the same methods as for the primary analysis. The positive predictive value of intervention and control group will also be calculated.

## 4. Power and Sample Size

The trial is powered to detect at the 5% significance level with 80% power in a two tailed test a difference in cancer detection rate between intervention and control group of one extra cancer detected per 2000 women screened. This would correspond to around 1000 extra cancers detected by screening in England each year. Power calculations used cancer detection rate in the control group (7.8 per thousand women screened) and cancer detection rate in the intervention group (8.3 per thousand women screened). These estimates of cancer detection rate are derived from data from a previous study.

ICC was calculated from previous data, using a logistic binomial-Gaussian model (method B) with 1000 Monte Carlo simulations. [7] Hence, using the derived ICC of 0.002 and a cluster (batch) size of 40 women, this then gives the design effect as 1.09. This gave an overall sample size required of 1,093,780 women, or 44 breast screening centres for 1 year (On the basis that in England there are 82 centres each screening around 25,000 women per year).

Trial Protocol CO-OPS Version 2

There is no adjustment for drop out or crossover because once the intervention is applied to a screening centre each batch will automatically be randomly assigned to intervention or control groups by the NBSS computer system, and the intervention applied automatically by that same system. However, there is a possibility that a small minority of records (circa 5000) will not be updated in time for the data collection. These will be considered missing at random as they will be all the cases from certain dates. A further 2000 women may be recalled for further tests and not attend their appointment. Furthermore, some radiologists may not read cases in the intended order, for example coming back to re-read difficult cases at a later time. This also is expected to be very rare in a busy screening centre, (circa 2250 in intervention arm), these cases will be included in the analysis. Therefore 1,100,780 cases are required to be randomised, equivalent to 44 screening centres for 1 year.

The same method was applied to detect a difference in cancer detection rate between intervention and control group of one fewer cancer missed per 2500 women screened. This gave an overall sample size required of 1.5 million women, or 44 breast screening centres for 1 year and 4 months.

Therefore 44 breast screening centres will be recruited to the trial, which will last for 1 year and 4 months. After the first year of the trial (allowing 2 months for follow up appointments to determine which women have cancer) the data for one year of screening at 44 centres will be downloaded, and analysis of the primary outcome of cancer detection rate, and the secondary outcomes to be completed. Analysis of missed cancer rates will not be until three years after completion of the whole trial duration.

There are 82 Breast Screening centres in England, of which 48 are fully digital, and 25 are partly digital. It is anticipated that by the start of data collection 64 centres will be fully digital. It is anticipated that it will take three months to enrol 44 centres and obtain local R&D approvals. Administering the trial at each centre will take the NHS staff no extra time commitment as it is fully computerised and will be automatically downloaded with their latest software update, which is anticipated will help reach recruitment targets.

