## 2 Trial Design

#### 2.1 Trial summary

The trial is a multi-centre cluster randomised parallel group superiority trial. The centres will be English Breast Screening centres with digital mammography equipment. The intervention is reversing the order in which the second radiologist reads each batch of mammograms. A cluster for randomisation is a batch of mammograms (circa 30 women's mammograms). The unit for analysis is the individual women's outcome.

The pre-pilot will be conducted in three screening centres for two weeks to ascertain the practical issues with implementation, and to test the Crystal report for data extraction. Concurrently a survey of all English breast screening centres will be conducted to ascertain key characteristics relevant to the trial which may differ between centres, such as the blinding of one reader to another's decision, and the method of arbitration used.

The trial will be implemented using an adaptation to the NBSS software used at participating centres.

The trial will last 16 months in 44 centres (1.5 million women). The first 12 months data (1.1 million women) will be collected from the NBSS database to determine whether the intervention affected cancer detection rate.

The full data set will be collected three years after the end of the study, to ascertain whether there was a decrease in rate of interval cancers (cancers presenting symptomatically in the three years after screening), and therefore whether the intervention reduced the number of cancers missed at screening.

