#### 2. Power and Sample Size

Currently, 14,700 cancers are detected by screening each year and the cancer detection rate is 7.8 per thousand women screened. (NHS Information Centre, 2012) To detect one extra cancer per 2000 women screened, this would increase the cancer detection rate to around 8.3 cancers per 1000 women screened. To detect this change of 0.5 cancers per 1000 women, for a two-tailed test at 80% power and 5% significance, 501,361 women are required in each arm, see figure 1.

However, as randomisation occurs at the batch level, collected data is clustered and must also be taken into consideration. The sample size of a clustered study must be increased by the Design Effect (DE), which is calculated as  $DE = 1 + (m - 1)\rho$  for a given ICC ( $\rho$ ) and cluster size (m).

ICC was calculated from previous data, using a logistic binomial-Gaussian model (method B) with 1000 Monte Carlo simulations. (Goldstein, 2002) Hence, using the derived ICC of 0.002 and a cluster (batch) size of 40 women, this then gives the DE as 1.09.

Therefore, the overall sample size required is for 1,093,780 women, or 44 breast screening centres for 1 year (On the basis that in England there are 82 centres each screening around 25,000 women per year).

There is no adjustment for drop out or crossover because once the intervention is applied to a screening centre each batch will automatically be randomly assigned to intervention or control groups by the NBSS computer system, and the intervention applied automatically by that same system. A woman could be lost to follow up if she is recalled from screening for further tests and does not attend her follow up appointment, however this is uncommon and so we have assumed low dropout rates for those who are recalled for further tests.

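### The 12-month sample size rests on 25,000 women per centre, which conflicts with other volumes in the documents. At the pre-trial volumes, power would be about 75–79%, not 80%.

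*Combined protocol and SAP*

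**What the plan says.** Protocol section 4 powers the primary comparison "at the 5% significance level with 80% power in a two tailed test", for detection rates of 7.8 against 8.3 per 1000 women screened. SAP section 2 states that "501,361 women are required in each arm" before clustering. Both documents apply a design effect of 1.09 and arrive at 1,093,780 women. Both then convert this to 44 centres for one year, "On the basis that in England there are 82 centres each screening around 25,000 women per year". The protocol adds about 7,000 women for late records and missed assessment appointments, which makes 1,100,780 to be randomised, still described as 44 centres for one year.

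The primary window is fixed by time. Protocol section 4 says that after the first year "the data for one year of screening at 44 centres will be downloaded, and analysis of the primary outcome of cancer detection rate" will follow. SAP section 3 likewise takes one year of data, but from 46 centres. Randomisation continues to 16 months because the missed-cancer outcome was sized separately at 1.5 million women.

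Other statements bear on centre volume:
- SAP section 2: "Currently, 14,700 cancers are detected by screening each year and the cancer detection rate is 7.8 per thousand women screened".
- Supplement 3, Table e1: mean 21,921 women per year (SD 10,355) in the 46 participating centres, for 2011-12.
- Protocol section 1.1: 2.3 million attenders per year projected after the age extension.
- Protocol section 4: one extra cancer per 2000 women would be around 1000 extra cancers a year in England.

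**The concern.** The step from women to centre-years uses a single volume, 25,000. Two other figures in the documents, one of them in the same SAP section, put the volume 8% to 12% lower. At 44 centres the conversion has no slack: 44 × 25,000 = 1,100,000, which is 780 below the randomised target. Any mean volume below 1,093,780 / 44 = 24,859 misses the analysed target as well.

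At stake is the stated 80% power for the primary outcome. Because the window closes at 12 months whatever has accrued, a shortfall in volume passes straight into lost power. Meanwhile the same centres continue to randomise women whose detection outcome the plan expects to have about two months after screening.

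**Working it through.** **Inputs.** p1 = 0.0078, p2 = 0.0083, two-sided 5%, 80% power, design effect 1.09, equal arms (protocol section 4, SAP section 2). Centres: 44 (protocol) or 46 (SAP section 3).

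**Reproducing the plan's figure.**
- p1(1−p1) + p2(1−p2) = 0.00773916 + 0.00823111 = 0.01597027.
- n per arm = (1.95996 + 0.84162)² × 0.01597027 / 0.0005² ≈ 501,395, against 501,361 stated.
- 501,361 × 2 × 1.09 = 1,092,967, against 1,093,780 stated. The figure reproduces to within 0.1%.

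**Volumes implied by the documents, per centre per year.**
- SAP section 2: 14,700 / 0.0078 = 1,884,615; / 82 = 22,983.
- Table e1: 21,921.
- Around 1000 extra cancers at one per 2000 women: 2.0 million; / 82 = 24,390.
- Projection in protocol section 1.1: 2,300,000 / 82 = 28,049.

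**Power at 12 months.** Power = Φ(0.0005 / SE − 1.96), where SE = √(0.01597027 / (N / 2 / 1.09)). For 44 centres at 22,983, N = 1,011,257 (from the unrounded volume). The effective n per arm is 463,879, SE = 0.00018555, 0.0005 / SE = 2.695, and power = Φ(0.735) = 76.9%. The last column is 12 × 1,093,780 / N.

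| Women per centre | Centres | N in 12 months | Power | Month at which 1,093,780 is reached |
|---|---|---|---|---|
| 25,000 (plan) | 44 | 1,100,000 | 80.2% | 11.9 |
| 22,983 (SAP section 2) | 44 | 1,011,257 | 76.9% | 13.0 |
| 22,983 | 46 | 1,057,223 | 78.7% | 12.4 |
| 21,921 (Table e1) | 44 | 964,524 | 74.9% | 13.6 |
| 21,921 | 46 | 1,008,366 | 76.8% | 13.0 |
| 21,921, one centre for 4 months only | 46 | 993,752 | 76.2% | 13.2 |
| 24,390 (1000 extra cancers) | 44 | 1,073,171 | 79.3% | 12.2 |
| 24,390 | 46 | 1,121,951 | 81.0% | 11.7 |
| 28,049 (projection) | 44 | 1,234,146 | 84.5% | 10.6 |
| 28,049 | 46 | 1,290,244 | 86.1% | 10.2 |

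The row with one centre at four months reflects the early withdrawal reported in Supplement 3: 45 × 21,921 + 21,921 / 3 = 993,752.

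**Sensitivity to the design effect.** The plan's formula gives 1 + 39 × 0.002 = 1.078, not 1.09. With 1.078, the Table e1 results are 75.4% (44 centres), 77.2% (46) and 76.6% (46 with the withdrawal), a change of about half a point.

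**All 16 months, for comparison.** At 21,921 per centre, 44 centres give 1,286,032 women (86.0%) and 46 give 1,344,488 (87.4%).

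**The case against.** The strongest reply is that both low volumes are old. Table e1 is for 2011-12, and the 14,700 cancers come from a 2010-11 report, while implementation was planned for 2013. A sample-size calculation needs a forecast. The protocol has one, 2.3 million attenders, and 25,000 lies between the past figures and that forecast. The SAP also works with 46 centres, which softens the loss. Protocol section 6.1 promises to monitor accrual by centre and act on a shortfall to protect power. Finally, the 12-month primary window is a deliberate choice, and the timetable (data in May 2014, write-up in September, health economics in December) depends on it.

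Much of this stands. A reader might infer that the trial will miss its sample size. The documents do not support that: they report no total of women analysed, and at the projected volume the target is passed before month 11. A reader might also infer that leaving months 13–16 out of the primary analysis is an error. It is not: the extra months were sized for missed cancers, and the 12-month analysis was sized separately.

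Three things are not answered. The sample-size sections use 25,000 without reconciling it with the projection or with the SAP's own cancer count. The monitoring promise has no numerical trigger and no rule to extend the primary window. Restriction to digital imaging and exclusion of technical recalls and repeat screens can only lower the count, although the documents give no figures for them and the loss may be negligible.

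**Conclusion.** The concern holds in conditional form. If centre volumes were those the documents report for the years before the trial, one year of data would give about 75–79% power (76–79% with 46 centres) in place of 80%. At the projected national volume it would give 84–86%, and at the 2.0 million implied by the protocol's 1000 extra cancers, 79–81%. The plan's claim therefore depends on a volume that its own documents put anywhere from 21,921 to 28,049, with no margin at 44 centres.

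The loss at the low end is moderate, about 1 to 5 points. These figures assume the planned rates, equal arms, a design effect of 1.09, and every woman counted in a centre's volume being eligible and analysable.

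**What to change.** In protocol section 4 and SAP section 2, give the source of the 25,000 figure and reconcile it with the 2.3 million projection, the SAP's 14,700 cancers at 7.8 per 1000, and Table e1. State 12-month power across that range, for the number of centres actually taking part.

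In protocol sections 2.1 and 4 and SAP section 3, before extraction, define the primary cut-off as the later of 12 months and the point when 1,093,780 analysable women have accrued. Base the rule on the pooled count alone, without sight of outcomes by arm, and say how the extra weeks apply across centres.

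The women needed are already being randomised within the planned 16 months, so no recruitment is added. The cost is some wording and, at the pre-trial volumes, a primary readout up to about two months later, with the write-up and the health economic model moving accordingly. At the projected volume nothing moves. Using all 16 months for the primary outcome (about 86–87% power at 21,921 per centre) is an option with a longer delay, not the correction of an error.

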## 5. Eligibility

## 5.1 Inclusion criteria

Screening centres taking part must use double reading of screening mammograms, and must have at least one piece of digital mammography equipment used for screening All women who receive mammography screening using digital equipment during the study period at the study centres.

## 5.2 Exclusion criteria

Centres which use single reading of mammograms

Centres which have no digital mammography equipment used for screening (the software intervention does not work on the old equipment)

Women who attend symptomatic breast clinics

#### 5.3 Post-randomisation withdrawals and exclusions

Centres participating may withdraw from the trial treatment, and/or the whole trial at any time without prejudice. No follow up data will be collected, only the initial survey results describing the centre characteristics will be used to analyse whether there are patterns in withdrawals from the trial, unless the centre requests that their data is not used in this way.

## 5.4 Compliance/contamination

Compliance is expected to be very high, as after centre level consent is given all implementation is automated. Therefore deviation from the protocol would be very difficult. Similarly contamination is not anticipated to be an issue as there is no method available to move cases between the intervention and control groups. However case order can be changed by selecting the ignore option rather than inputting a screening result and reviewed at a later stage, or a result could be inputted and then revised later. These things would change the reading order and produce some level of contamination. This will be ameliorated by analysing based on intended order of reading. Data will be collected on actual reading order also to measure levels of contamination and their effect on outcomes. These effects are expected to be extremely small (of the order of once per 500 cases) because screening is a fast moving high volume activity and there is no time in practice to come back to cases at a later stage.

#### 6. Consent

Informed consent will be obtained at the centre level, by the director of the service and the lead radiologist. These are usually the same person but if they are not the consent of both will be sought. Consent will be required at the centre level rather than the patient or radiologist as it is at this level that the intervention is applied. The intervention can be considered an alternative and at least equivalently good form of standard practice, as nothing about how the mammograms are reviewed and evaluated changes, just the order in which they are assessed.

Directors of breast screening centres will be contacted in the first instance by email introducing the study with a copy of the participant information sheet and informed consent form attached. They will then receive a follow up phone call one week later. Each centre will be offered a copy of the research protocol and IRAS ethics form, and a visit from one of the investigation team to introduce the study if they wish. The study software which will run the trial will be embedded in the NBSS software in every English breast screening as part of the routine updating of the NBSS system. This software will remain inactive until a signed consent form is received from that centre, at which point it can be activated simply and quickly. The study can commence in each centre by simply changing the software settings to activate the intervention.

In the unlikely event that information becomes available may be relevant to the participant's willingness to continue in the trial, for example findings from other research studies, then the directors of every participating breast screening centre will be informed immediately by email and follow up phone call.

#### 6.1 Recruitment and Randomisation

The rate of accrual will be monitored at the centre level, if it falls appreciably below the projected level, the reasons will be identified and remedial actions taken in order to protect the power of the trial and alleviate concerns about selective entry and other aspects of quality.

Randomisation will be automatically computer generated at the point at which the batch is ready to be read on the NBSS system. The random number generation will be using the root of the time at which randomisation is required. Only batches of cases to be read as part of the NHS breast screening programme will be randomised. Cases from symptomatic clinics will be excluded prior to randomisation.

## 6.2 Blinding

There is no expected placebo effect in this trial. No elements of standard practice are to be changed as part of the trial except reading order, to test whether the intervention would be effective in normal practice. The women screened will not be aware whether their mammograms are read as part of an intervention or control batch. The radiologists and radiography advanced practitioners when acting as second reader are not blinded to reading order, but they are blinded to trial arm because both intervention and control groups include reading forwards and backwards. The statistician will be blinded to treatment groups until analysis is complete.

## 7. Project Timetable and Milestones

## Year 1

August 2012: Software developed, ethical approvals complete and trial registered December 2012: Pilot complete and 44 sites recruited

#### Year 2

Implementation in all 44 sites throughout 2013

#### Year 3

May 2014: 1 year data collected in 44 centres.

September 2014: Write up complete

December 2014: Heath economics analysis complete

#### Year 6

Collection and analysis of interval cancer data. Follow on funding is required to proceed with this part of the project.

#### 8. Protocol Amendments

Version 2.0: agreed on 24th July 2013 – number of centres increased from 36 to 44. (Coventry and Warwickshire REC on 12th July 2013 approved minor amendment to increase the number of centres from 36 to 44).

#### 1. Dates of amendments and decisions

24/10/12 ISRCTN application submitted

26/3/2013 ISRCTN application accepted (ISRCTN46603370)

24/7/2013 Statistical Analysis plan agreed by Trial Steering Committee

10/1/2014 Protocol published (Taylor-Phillips et al. 2014)

16/1/2014 Planned reporting of additional details of clusters added (table 1 added) to describe external validity (Eldridge et al. 2008)

20/3/2014 Agreement at Trial Steering Committee to add analysis 3. Agreement that this is exploratory follow-up analysis which will not form part of the analysis in the main paper

2/4/2014 Trainees at one participating centre are logging in as qualified film readers. This causes a subset of cases intended for intervention arm 1 to move to intervention arm 2. Decision by Trial Steering Committee not to change analysis as they remain in the intervention arm.

15/9/2014 Page 4 single reader, >2 readers, barcode reading, and administrator entering results misclassified 'protocol violation' corrected to 'non-compliance'.

23/10/2014 First data collected from breast screening centres

#### 2. Power and Sample Size

Currently, 14,700 cancers are detected by screening each year and the cancer detection rate is 7.8 per thousand women screened. (NHS Information Centre, 2012) To detect one extra cancer per 2000 women screened, this would increase the cancer detection rate to around 8.3 cancers per 1000 women screened. To detect this change of 0.5 cancers per 1000 women, for a two-tailed test at 80% power and 5% significance, 501,361 women are required in each arm, see figure 1.

However, as randomisation occurs at the batch level, collected data is clustered and must also be taken into consideration. The sample size of a clustered study must be increased by the Design Effect (DE), which is calculated as  $DE = 1 + (m - 1)\rho$  for a given ICC ( $\rho$ ) and cluster size (m).

ICC was calculated from previous data, using a logistic binomial-Gaussian model (method B) with 1000 Monte Carlo simulations. (Goldstein, 2002) Hence, using the derived ICC of 0.002 and a cluster (batch) size of 40 women, this then gives the DE as 1.09.

Therefore, the overall sample size required is for 1,093,780 women, or 44 breast screening centres for 1 year (On the basis that in England there are 82 centres each screening around 25,000 women per year).

There is no adjustment for drop out or crossover because once the intervention is applied to a screening centre each batch will automatically be randomly assigned to intervention or control groups by the NBSS computer system, and the intervention applied automatically by that same system. A woman could be lost to follow up if she is recalled from screening for further tests and does not attend her follow up appointment, however this is uncommon and so we have assumed low dropout rates for those who are recalled for further tests.

